**Time to discharge from hospital, time to the 2 most favorable categories of the primary ordinal outcome:** We expect that by Day 28, almost all participants will be discharged from the hospital. Similarly, we expect most participants will be in in one of the 2 most favorable categories of the primary ordinal outcome by Day 28. In the ACTT-1 trial, in the subset of participants who entered the trial with disease severity similar to our eligibility criteria (ACTT-1 ordinal outcome categories 4+5), 94.7% had been discharged from the hospital by Day 28. This percentage was similar for the ACTT-1 definition of “recovery” that include a small percentage of participants who were hospitalized but no longer requiring medical care. Comparing the hVIG versus placebo groups for time to hospital discharge, our study is powered to detect a relative rate ratio (RRR) of 1.3 with 80% power and a significance level of 0.05. The power calculations assume that the RRR is approximately constant to Day 28, the overall cumulative percentage discharged (pooled across treatment groups) by Day 28 is 94% and that between 2.5 and 3% withdraw consent or are lost to follow-up by Day 28. We assume power is similar for time to the 2 most favorable outcomes of the primary ordinal outcome.

**Hospitalization status:** Comparing the hVIG versus the placebo+SOC groups for the hospitalization status (a binary outcome, alive and discharged from the hospital to home or rehabilitation versus dead or hospitalized) on Day 7, the total sample size of 500 participants is sufficient to detect an increase in the proportion discharged to

58% in the hIVIG group from 45% in the placebo group (OR=1.7), with 80% power. Similarly, the study has 80% power to detect an increase to 81% in the hIVIG group compared with 70% in the placebo group (OR=1.85) at Day 14. Corresponding estimates from the ACTT-1 trial were 51% discharged on Day 7, and 77% on Day 14, for participants that were similar to ours and randomized to the remdesivir arm (confidential data; personal communication). Our hypothesized percentages are slightly lower, because our eligibility criteria allow for use of high-flow oxygen, in addition to the ACTT-1 ordinal categories 4+5. Power calculations assume that the treatment groups are compared by intent-to-treat.

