### 7.1 Inclusion Criteria

In order to be eligible to participate in this study, a participant must meet all of the following criteria:

1. SARS-CoV-2 infection documented by PCR or other nucleic acid test (NAT) within 3 days prior to randomization OR documented by NAT more than 3 days prior to randomization AND progressive disease suggestive of ongoing SARS-CoV-2 infection
2. Symptomatic COVID-19 disease
3. Duration of symptoms attributable to COVID-19  $\leq 12$  days
4. Requiring inpatient hospital medical care for clinical manifestations of COVID-19 (admission for public health or quarantine only is not included)

5. Age  $\geq$  18 years
6. Willingness to abstain from participation in other COVID-19 treatment trials until after study Day 7
7. Provision of informed consent by participant or legally authorized representative

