## APPENDIX F CLINICAL CATEGORICAL DEFINITIONS FOR ORDINAL OUTCOME

*Each participant is categorized in the highest applicable category.*

Ordinal Category	Categorical Description	Categorical Definition*
7	Death	Death
6	End-organ failure	Currently requiring invasive assisted ventilation, extracorporeal membrane oxygenation, mechanical circulatory support, vasopressor therapy or renal replacement therapy
5	Life-threatening end-organ dysfunction	Currently requiring non-invasive assisted ventilation or high-flow oxygen or Extra-pulmonary: Symptoms and signs of an acute stroke (NIHSS > 14)
4	Serious end-organ dysfunction	Currently requiring supplemental oxygen ( $\geq 4$ liters/min, or $\geq 4$ liters/min above premorbid requirements**) but not high-flow oxygen or Any of symptoms or signs of the following extra-pulmonary conditions: Stroke (NIH Stroke Scale/Score [NIHSS] $\leq 14$ ), meningitis, encephalitis, or myelitis, myocardial infarction, myocarditis, pericarditis, or New York Heart Association Class III or IV congestive heart failure, arterial or deep venous thrombosis including pulmonary embolism.
3	Moderate end-organ dysfunction	Requiring supplemental oxygen < 4 liters/min, or < 4 liters/min above premorbid requirements**
2	Limiting symptoms due to COVID-19	Symptomatic and currently unable to independently undertake usual activities
1	No limiting symptoms due to COVID-19	Can independently undertake usual activities with minimal or no symptoms

*\*Continued hospitalization or presence in a particular category of inpatient facility (e.g. intensive care or high dependency) is not used to divide these categories, as indication for continued hospitalization among recovering COVID patients is intrinsically subjective, in part determined by social and financial factors, and varies markedly across the globe.*

*\*\* Premorbid requirement refers to requirements prior to the development of COVID-19, for example in patients with chronic obstructive pulmonary disease, other chronic pulmonary diseases, or oxygen requirements related to altitude.*

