### 1.2.3 Summary of Baseline Characteristics

Selected baseline characteristics that were considered (as of March 23, 2021) in revising the SAP are given below.

1. As noted above, participants are from 11 countries. Numbers enrolled by country are: Denmark (77), Germany (10), Spain (65), Greece (70), UK (19), Indonesia (33), Argentina (4), Israel (6), Japan (15), Nigeria (41), and U.S. (253).
2. Median (25th, 75th percentile) of age is 59 (50, 70) years.
3. Median (25th, 75th percentile) of symptom onset is 8 (6, 10) days.
4. Oxygen status (above pre-COVID-19 requirement): 28% were not receiving oxygen; 34% were receiving < 4 L/min; 28% were receiving ≥ 4 L/min; and 10% were receiving high-flow oxygen.
5. 541 (93%) received remdesivir prior to randomization or on the same day as randomization as part of SOC.
6. 329 (56%) were receiving corticosteroids at entry; 48 (84%) among those on high-flow oxygen and 229 (62%) among those on supplemental oxygen.
7. 355 (60%) were receiving heparin (prophylactic, intermediate, or therapeutic dose) at entry.
8. Median (10th, 25th, 75th, 90th percentile) BMI is 29.8 (23.0, 25.8, 34.7, 40.2) kg/m^2.
9. Selected diagnoses (% reported) collected as part of a medical history and an elevated BMI are summarized below:
  - o Asthma (10%)
  - o Cerebrovascular event (1%)
  - o COPD (6%)
  - o Diabetes (28%)

- Heart failure (4.6%)
- Hepatic impairment (2%)
- HIV (2%)
- Hypertension requiring medication (42%)
- Immunosuppressive disorder other than HIV (1%)
- Malignancy (4%)
- MI (3%)
- Renal impairment (7%)
- BMI  $\geq$  30 kg/m^2 (49%)

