*size of 579 participants (the estimated number of participants in the mITT analysis) is sufficient to detect a decrease to 6.6% in the hVIG group compared with 13.6% in the placebo group (difference 7.0%) with 80% power. A decrease from 13.6% to 8.8% as in Table 1 (OR = 1.61) can be detected with power of 45%.*

**Time to the two most favorable categories of the primary ordinal outcome (first occurrence):** We expect that by Day 28, almost all participants will be discharged from the hospital. Similarly, we expect most participants will be in in one of the two most favorable categories of the primary ordinal outcome by Day 28. In the ACTT-1 trial, in the subset of participants who entered the trial with disease severity similar to our eligibility criteria (ACTT-1 ordinal outcome categories 4 and 5), 94.7% had been discharged from the hospital by Day 28. This percentage was similar for the ACTT-1 definition of “recovery” that includes a small percentage of participants who were hospitalized but no longer requiring medical care. Comparing the hVIG versus placebo groups for time to the 2 most favorable categories, our study is powered to detect a relative rate ratio (RRR) of 1.3 with 80% power and a significance level of 0.05. *The power calculations assume that the RRR is approximately constant to Day 28, the overall cumulative percentage in the two most favorable categories (pooled across treatment groups) by Day 28 is 81% and that between 2.5 and 3% withdraw consent or are lost to follow-up by Day 28.*

**Two most favorable categories at Day 7:** *Comparing the hVIG versus the placebo+SOC groups for the percentage in the two most favorable categories (a binary outcome) on Day 7, the total sample size of 579 participants is sufficient to detect an increase in the this percentage from 54% in the placebo group to 65.4% in the placebo group (as in Table 1) with 80% power.*

**Hospitalization status at day 14:** *The study has greater than 80% power to detect an increase to 87% in the hVIG group compared with 77% in the placebo group for the percentage discharged at Day 14. Estimates from the ACTT-1 trial used for the placebo group were 51% discharged on Day 7, and 77% on Day 14, for participants that were similar to ours and who were randomized to the remdesivir arm (confidential data; personal communication). Power calculations assume that the treatment groups are compared by mITT.*

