*For outcomes 11-14, time-to-event methods that take into account the competing risk of death will be used. Specifically, Gray's test with  $\rho=0$ , the Fine-Gray model, and the Aalen-Johansen estimator for the cumulative incidence curve are the competing risk equivalents to the log-rank test, Cox proportional hazards model, and the Kaplan-Meier estimator for the cumulative proportion of participants with the event, respectively. Gray's test and the Fine-Gray model will be stratified by study product/matching placebo group and baseline ordinal category.*

*Additionally, as a sensitivity analysis for the analysis of time-to-discharge and days outside the hospital we will exclude participants from the 5 sites where no participants were discharged prior to Day 7.*

15. Days alive outside of a hospital through Day 28
16. Days alive and able to independently undertake usual activities with minimal or no symptoms through Day 28
17. Days alive and out of the hospital or able to independently undertake usual activities with minimal or no symptoms through Day 28 (whichever lead to greatest time)

*These outcomes (15-17) have been used in other trials of therapeutics for COVID-19. We will sum the number of days that each individual spends outside a short-term acute care hospital up to 28 days. A person who dies within 28 days will be assigned a value 0, consistent with the approach taken*

*in trials of intensive care-based interventions. We will present the mean and median days by group. We will test the hypothesis of no mean difference between arms using methods for continuous outcomes (ANCOVA models), with baseline baseline ordinal outcome group and study product/matching placebo group as covariates. Because the residual distribution is unlikely to be normally distributed, we will use robust or sandwich standard errors. This analysis will be undertaken only when complete follow-up data are available. The outcome does have limitations due to its handling of death and withdrawal. We expect that there will be minimal missing data but may use multiple imputation for the final analysis.*

18. Change in immunoglobulin levels (IgG, IgG subclasses, IgM, IgA) and neutralizing antibody titres from baseline to Days 1, 2, 3, 7, 28 and 90.

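### The 80% power for time to the two most favorable categories counts about 162 participants already in those categories at entry; on the at-risk set it is about 62-67%

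*SAP*

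**What the plan says.** SAP 1.4 lists this as a key secondary outcome and defines it by first entry to the state: "Time to the two most favorable categories of the primary ordinal outcome (first occurrence"). Its power statement is "time to the 2 most favorable categories, our study is powered to detect a relative rate ratio (RRR) of 1.3 with 80% power", at a 0.05 significance level. The stated inputs are an RRR roughly constant to Day 28, 2.5-3% loss, and that "the overall cumulative percentage in the two most favorable categories (pooled across treatment groups) by Day 28 is 81" per cent.

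SAP 7.4 (outcome 11) analyses it with Gray's test and the Fine-Gray model, and says that "the Fine-Gray model will be stratified by study product/matching placebo group and baseline ordinal category". SAP 7 makes the whole mITT set (579 participants, SAP 4) the default population and uses two-sided 0.05 tests.

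On entry status, SAP 1.2.3 reports that "28% were not receiving oxygen". Protocol Appendix F defines category 2 as "Symptomatic and currently unable to independently undertake usual activities". Supplemental oxygen begins at category 3.

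The power figure comes from Protocol 5.5.3, where it was worked out for time to discharge. The protocol then added: "We assume power is similar for time to the 2 most favorable outcomes of the primary ordinal outcome".

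**The concern.** A time-to-event power calculation should count only people who can still have the event. Everyone is at risk of discharge at entry, because inclusion criterion 4 requires it: "Requiring inpatient hospital medical care for clinical manifestations of COVID-19". Reaching category 1 or 2 is different, since more than a quarter of participants appear to have been there at randomization. The SAP updated the event percentage and sample size but shows no sign of removing them.

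Two things follow. First, the stated power is too high, so a null result on a key secondary outcome would be read as stronger evidence of no effect than it is. Second, SAP 1.4 and 7.4 do not say whether these participants are left out, counted as events on Day 0, counted from Day 1, or required to worsen first. Two analysts could therefore produce different cumulative incidence curves from the same data.

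**Working it through.** **Inputs.** RRR 1.3, 80% power, 81% by Day 28, 2.5-3% loss (midpoint 2.75%): SAP 1.4. Two-sided 0.05: SAP 7. 1:1 allocation: SAP 1.4. N = 579: SAP 4. Share off oxygen, 28%: SAP 1.2.3.

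**Formula.** Schoenfeld, 1:1: power = Φ(√(D/4) × ln 1.3 − 1.96), where D is the number of events. For 80% power, D = 4 × (1.96 + 0.8416)² / (ln 1.3)² = 456.

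**The plan's own figures.**
- Protocol, time to discharge: 500 x 0.94 x 0.9725 = 457 events, power 80.1%.
- SAP, time to categories 1-2: 579 x 0.81 x 0.9725 = 456 events, power 80.0%.
- With 500 participants, 81% gives only 74-75%. With all 593 randomized it gives 80.8-82.0%. The 80% therefore needs essentially everyone to be at risk.

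**Number already in the state.** 0.28 x 579 = 162, leaving 417. As a cross-check, the corticosteroid counts in SAP 1.2.3 imply 48/0.84 = 57 on high-flow oxygen and 229/0.62 = 369 on other supplemental oxygen. That leaves 593 − 57 − 369 = 167 off oxygen, again 28%.

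**Power on the at-risk set.** The SAP does not say what the 81% is a percentage of, so both readings are shown.

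| Reading of the 81% | Events, no loss | Events, 2.75% loss | Power | RRR detectable at 80% |
|---|---|---|---|---|
| Includes the 162 | 469 − 162 = 307 | 298 | 62.0-63.2% | 1.38 |
| Applies to the 417 only | 0.81 x 417 = 338 | 328 | 66.2-67.4% | 1.36 |

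**Ceiling.** If every one of the 417 had the event, power would be 76% (75% with 2.75% loss). On this set 80% at RRR 1.3 cannot be reached at any event rate.

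**Counting the 162 as Day 0 events.** A stratum in which everyone has the event at the same time adds nothing to a stratified test. A simulated log-rank test stratified by baseline category (daily grid, 2.75% loss) gave about 80% with all 579 at risk. With 162 Day 0 events it gave about 62% and 67% under the two readings. Excluding the 162 gives nearly the same.

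**Sensitivity (assumed values, not in the documents).**
- If 5-10% of the 162 were in category 4 for an extra-pulmonary condition, power is 63-68%.
- If events count only from Day 1 and 10-20% of the 162 had worsened by then, an effective-event count gives about 66-73%. In simulation, power is about 61-67% if treatment has had no effect by Day 1, and about 70-79% if the full RRR is already present on Day 1.
- In the cases simulated, about 80% was reached only with around 30% worsening by Day 1, the full effect within that day, and the 81% applying to the others alone.

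**The case against.** The arithmetic is hard to dispute, but several points limit it.

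- **N is inferred.** The SAP paragraph gives no sample size for this outcome; 579 is named only for its neighbours. That all 579 were counted rests on a numerical match. This stands as a caveat. However, the ceiling of 76% means that no count restricted to the at-risk set could give 80%.
- **Oxygen status is not ordinal category.** The 28% is measured relative to the pre-COVID-19 requirement, and some people off oxygen could be in category 4 for an extra-pulmonary condition. This also stands, but the exclusions for recent thrombotic or coronary events and for NYHA class III-IV heart failure make large numbers unlikely, and the effect is small.
- **The 62-67% presumes exclusion or Day 0 counting.** Day 1 counting could give more, and the SAP's power paragraph does assume a roughly constant RRR. This is the strongest point. But no Day 1 rule is stated, the worsening rates needed are assumptions, and SAP 1.4 itself expects clinical effects to take a few days.
- **The practical effect is limited.** Enrollment had closed, secondary outcomes are described as supportive and unadjusted, and the SAP openly reports 45% power for another key secondary outcome under Table 1. All true. It limits the weight of the point but does not make the stated figure right.
- **Part of the text was not available.** SAP 1.2.5 (pooled follow-up results) was not in the copy read and may give the source of the 81%. Both readings of that percentage fall well short of 80%.

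**Conclusion.** The concern holds and should be fixed. The stated 80% relies on about 162 participants who were already in the target state and from whom the planned stratified test gains little or nothing. Power for RRR 1.3 is about 62-67%, and the RRR detectable with 80% power is about 1.36-1.38.

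This rests on three assumptions: being off oxygen is a close proxy for category 1 or 2; those participants are excluded or counted at Day 0; and the log-rank approximation serves for Gray's test. The statement that no handling rule exists is limited to the SAP text available. The primary endpoint is not affected, and the stratified tests remain valid.

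**What to change.** Before unblinding:

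1. In SAP 7.4, state that outcome 11 is analysed among participants in category 3 or worse at entry, as a named exception to the mITT default. Those in categories 1-2 at entry remain in the primary analysis and in the Day 7 status outcomes. Category 2 entrants also remain in outcomes 13 and 14; any category 1 entrants already meet those endpoints, so the same text should cover them.
2. In SAP 1.4, restate the power as about 62-67% for RRR 1.3 (detectable RRR about 1.36-1.38) and give the denominator of the 81%.
3. For completeness, give outcome 10 (time to the three least favorable categories) an at-risk set too: participants not in categories 5-7 at entry. About 10% (0.10 x 579 = 58) entered on high-flow oxygen, which is already category 5. No power is claimed for that outcome, and progression of these participants is captured by outcomes 4 and 9.

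An explicit Day 0 convention with the corrected power would also remove the ambiguity and gives nearly the same power, but the curves would then start near 28% in both groups.

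The cost is two or three sentences and one restated figure, with no new data. The drawbacks are a smaller denominator (about 417), a less favourable stated power, and an estimate that applies only to participants in category 3 or worse at entry.

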## **Data and Safety Monitoring**

An independent Data and Safety Monitoring Board (DSMB) will review interim data and use pre-specified guidelines for early termination of the trial or protocol modification.

## **2 Interim DSMB Reviews: Goals and Format**

### **Goals of the interim reviews:**

- Protect the safety of study participants.
- Advise on stopping or modifying the trial for efficacy, for patient safety in case of emerging data on harm, or for futility.
- Review the conduct of the trial

The DSMB will conduct frequent safety reviews. The DSMB will review safety data for the first 20 to 30 participants randomized after they have been followed for 7 days. Thereafter, the DSMB will be asked to review safety data at 30 day intervals. The blinded sample size re-estimation will occur after 150 participants have been followed for 7 days. Futility reviews will be presented to the DSMB for the primary endpoint after 50% of information time (based on the percentage of participants who have completed 7 days of follow-up) is available.

**The DSMB may request interim reports on safety and efficacy at any time.**

Review meetings will typically consist of an Executive session (optional; closed), open session, closed session, and a second open session to give feedback to study leadership (optional).

**Masking of treatment group labels in interim reports:** In the open reports, any data reports will be pooled across the two treatment groups. In the closed reports, treatment group labels will be masked; for example as “Group A” versus “Group B”. The treatment group labels will be consistent across all analyses and over subsequent reports. With each closed report, the DSMB will receive a separate, encrypted file that un.masks the treatment group labels. This procedure ensures that the DSMB has the full information to weigh benefit versus harm.

**Open report to the DSMB**

The open reports will contain:

- A synopsis of the trial design and current status of the trial
- Responses of the study team to DSMB recommendations
- A summary prepared by the study leadership including any relevant emerging data from other studies
- Data summaries for enrollment (including enrollment by hVIG product/matching placebo group) and eligibility violations (Section 3), baseline characteristics (Section 5) and protocol deviations
- Summary reports for data completeness and study conduct (including number infused), pooled across treatment groups (see Sections 6 and 8)
- Unanticipated problems

All data summaries in the open report will be pooled across treatment groups. The open report will be prepared by the blinded statisticians in cooperation with the unblinded statisticians. In addition to the DSMB, open reports will be provided to the study team, and posted on the study website following the DSMB meeting for access by study investigators.

While the study is ongoing, summaries by treatment group, and comparisons of the hVIG versus placebo are restricted to the confidential closed report to the DSMB.

Additionally, all summaries of follow-up data other than the data completeness and study conduct reports (pooled across the two treatment groups) will be restricted to the confidential closed report. For the planned sample size re-estimation, the pooled proportion of participants in each level of the seven-level ordinal outcome at Day 7 will be provided to the blinded study statisticians and study leadership.

### **Closed report to the DSMB**

All data summaries in the closed report will be by (masked) treatment group. Comparisons between treatment groups will be by intention-to-treat among those randomized (efficacy outcomes) and among those receiving any infusion (safety outcomes). Specific details are given in the indicated sections. The closed reports for a full review will contain:

- Specific data summaries requested by the DSMB or study leadership
- Data summaries in the open report, by treatment group (enrollment, baseline characteristics, eligibility violations)
- Data summaries to assess safety of the investigational treatment including infusion reactions, AEs, SAEs, deaths, composite primary safety outcome are described in Section 7.2. Data summaries for the primary “efficacy outcomes”, and selected secondary outcomes will also be included in each report because these data contain information about the risk/benefit profile of hIVIG. Analyses are described in Sections 7.1, 7.4, and 7.5.
- Summaries on data completeness and study conduct, described in Section 8.
- Interim monitoring boundaries for the primary safety outcomes (Section 7.2).
- Interim monitoring boundaries for efficacy when sufficient data have accrued (Section 7.1).
- Futility analyses when sufficient data have accrued (Section 7.3).
- Listings of incident (new or increase in severity from baseline) grade 3 and 4 adverse events, serious adverse events (SAE), unanticipated problems (UP), suspected unexpected serious adverse reactions (SUSAR), and deaths (Section 7.2).

